13.4.2 Primary Analysis of Primary Endpoint

Part 1

Descriptive statistics will be used to summarize the proportion of participants in each cohort who experience at least one Grade 3 or greater adverse event during study participation for all participants in the safety population. The primary analysis of efficacy and safety endpoints will be conducted after all participants in Cohort 1a and 1b complete the Week 48 assessments or are withdrawn from the study.

Part 2

The primary endpoint for Part 2 is disease response at 48 weeks, defined as the percent improvement in the IgG4-RD RI score over baseline:

$$\% \text{ Improvement in IgG4RD RI}_{\text{Week 48}} = 100 * \left(\frac{\text{IgG4RDRI}_{\text{Baseline}} - \text{IgG4RDRI}_{\text{Week 48}}}{\text{IgG4RDRI}_{\text{Baseline}}} \right)$$

For participants whose IgG4-RD RI score is worse (e.g. higher) at week 48 than baseline, their % Improvement in IgG4-RD RI_{Week 48} will be considered 0%. Additionally, participants who use glucocorticoids or other immunosuppressants beyond that permitted by protocol, or who experience a disease flare as defined in Section 3.5.3 at any time point before 48 weeks will be defined as achieving no disease response (0%).

The observed levels of disease response at 48 weeks will be summarized by arm in the mITT population as the median, interquartile range, and range. A between-group comparison of the assessment of disease response at 48 weeks will be performed using a Wilcoxon-Mann-Whitney test with a two-sided Type I α of 0.05, and will be reported with a two-sided 95% confidence interval for the Mann-Whitney parameter (Section 13.6) derived under the proportional odds assumption [41]. The primary analysis of disease response will treat all participants who drop out of the study prior to reaching week 48 for any reason, including a disease flare, initiation of non-protocol therapy, or any other reason to cause them to be unevaluable using the IgG4 Responder Index, as having no disease response (0% improvement) for the primary endpoint. The primary analysis will be conducted after all participants in Cohort 2 complete the Week 48 assessments or are withdrawn from the study.

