3.7 Stratification, Randomization, and Blinding/Masking

In Part 2, after participants sign the consent form, those eligible will be randomized in a 2:1 ratio to receive elotuzumab versus placebo. Randomization will be stratified by whether participants have newly-diagnosed or relapsing disease at entry.

Randomization will be accomplished through a password-protected, web-based, randomization system. The investigators, clinic personnel, and participants will not be informed regarding the intervention assignment until the study is unblinded. Laboratories performing assays for this protocol will be masked to the identity and group assignment of biological materials to be studied.

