13.3 Measures to Minimize Bias

In Part 2, randomization to treatment allocation will be performed to minimize bias in the comparison of the primary and secondary efficacy endpoints. Randomization will be stratified by newly-diagnosed or relapsing disease at entry to minimize confounding with the effects of treatment. In addition, the use of a placebo-controlled design for elotuzumab will minimize the risk of ascertainment bias in the IgG4-RD Responder Index and assessments of efficacy and safety endpoints in Part 2 of the study.

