13.4.3 Supportive Analyses of the Primary Endpoint

A supportive analysis of the primary endpoint will consider participants who drop out of the study prior to reaching week 48 without evidence of disease flare, initiation of non-protocol therapy, or other indications of increased disease activity as missing-completely-at-random (MCAR). Descriptive statistics and the Wilcoxon-Mann-Whitney test will be repeated in the subgroup of the mITT population excluding participants with data MCAR. A masked data review panel will evaluate participant disposition and all disease activity assessments in a blinded manner to define the types of missing data. In addition, analysis of the primary endpoint will be repeated as a van Elteren test with a covariate for the stratification factor of newly-diagnosed versus relapsing disease at study entry. As an additional supportive analysis which does not assume data are MCAR, a two-dimensional tipping point analysis of missing data will be conducted. Additional details on supportive analysis will be specified in the Statistical Analysis Plan.

Supportive analyses of the primary endpoint will be repeated in the PP populations and as a preplanned subgroup analysis in participants who are identified as having elevated serum IgG4 level prior to initiation of study therapy. The subgroup is defined as any serum IgG4 concentration greater than 1.5 times the upper limit of normal that is obtained within 6 months of the Baseline visit or at the baseline assessment of Serum IgG subclasses.

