13.4.4 Analyses of Secondary and Other Endpoints

The key secondary endpoint for Part 2 is complete response at 48 weeks, defined as an IgG4-RD RI Score of 0 and a glucocorticoid dose of 0 mg/day and no flare since beginning treatment. A fixed sequence testing procedure will be conducted with the primary efficacy endpoint, to control the overall Type I error rate at 0.05. Specifically, if the between-group comparison of disease response at 48 weeks reaches statistical significance, a comparison of the rates of complete remission at 48 weeks will be performed using a Fisher's Exact test with a two-sided Type I α of 0.05. If the between-group comparison of disease response at 48 weeks fails to reach statistical significance,

inferences on complete remission will be supportive without overall Type I error control. The proportion in complete remission in each arm will be reported with two-sided 95% Clopper-Pearson confidence intervals. All participants in the mITT population who drop out of the study prior to reaching week 48 for any reason, including a disease flare, initiation of non-protocol therapy, or any other reason to cause them to be unevaluable using the IgG4 Responder Index, will be defined as not achieving complete remission.

All inferential analyses for the additional secondary efficacy endpoints are considered supportive; p-values for test of differences among groups will be presented without adjustment for multiple comparisons. All secondary endpoints will be analyzed in the mITT and PP populations, and in the subgroup with elevated serum IgG4 level prior to initiation of study therapy.

For all dichotomous efficacy endpoints, Fisher's Exact tests will be conducted and two-sided 95% Clopper-Pearson confidence intervals will be reported.

Frequency counts of the number of disease flares and the number of organ sites with disease-related damage will be reported by arm, and between-group comparison will be performed using Fisher's Exact Test.

For secondary continuous efficacy endpoints, including the Physician Global Assessment and Patient Global Assessment, descriptive statistics will be used to summarize the distribution of scores in each arm. The absolute change from baseline will be analyzed using an analysis of covariance model (ANCOVA) with treatment allocation as the independent variable.

Treatment group differences for the safety endpoints will be compared using a Fisher's exact test.

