13.6 Statistical Hypotheses

In Part 2, the null hypothesis for the Wilcoxon-Mann-Whitney test is defined according to the Mann-Whitney parameter [42], as the probability that a randomly selected individual in the treatment arm will have a better outcome than a randomly selected individual in the control arm, with an adjustment for ties [43]. Specifically, let X_E be a random outcome from a population to receive elotuzumab, and X_P be a random outcome from a population to receive placebo. Then,

$$H_0: \delta = Pr(X_E > X_P) + \frac{1}{2} \cdot Pr(X_E = X_P) = 0.5$$

The alternative hypothesis is that there is unequal probability that the addition of elotuzumab treatment is superior to the addition of placebo in achieving disease response at 48 weeks.

$$H_1: \delta = Pr(X_E > X_P) + \frac{1}{2} \cdot Pr(X_E = X_P) \neq 0.5$$

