In Part 2, a 2:1 allocation ratio was selected to evaluate aspects of treatment, including both safety of the combination of elotuzumab with prednisone and the exploratory objectives of the study. The sample size for Part 2 was determined by specifying the natural parameter to the Wilcoxon-Mann-Whitney test of $\delta = 0.75$ would warrant further investigation of the agent. The probability of 0.75 was selected as a target effect size for this proof-of-concept study using a simulation study based on the scale of the IgG4 RI and variable rates of improvement and achievement of complete remission. Under Gaussian assumptions, the Mann-Whitney parameter is equivalent to a mean difference of 1.0 standardized units. Using the formula from Noether [44], and with the desired allocation ratio of 2:1 to receive elotuzumab versus placebo in addition to the prednisone-taper, $N = 63$ participants ($n_E = 42$, $n_P = 21$) would provide 90% power to detect the target effect-size. For the secondary efficacy endpoint of complete remission at 48 weeks, Yunyun et al. [8] reported a complete remission rate at 6 months of approximately 25% with glucocorticoid treatment alone. With the target sample size of 63 participants, a Fisher exact test using $\alpha = 0.05$ (two-sided) will have at least at 80% power (exact power = 0.826) to detect an improvement from 25% to 65% in the complete remission rate at 48 weeks with the addition of elotuzumab.

14 Identification and Access to Source Data

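### Randomisation is stratified by newly-diagnosed versus relapsing disease, but the deciding primary test ignores the strata and gives up some power if disease history is prognostic

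*Combined protocol and SAP*

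**What the plan says.** Section 3.7 sets the design: "Randomization will be stratified by whether participants have newly-diagnosed or relapsing disease at entry". Section 13.3 gives the reason: "Randomization will be stratified by newly-diagnosed or relapsing disease at entry to minimize confounding with the effects of treatment". It is the only stratification factor.

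Section 13.4.2 specifies the primary test: "A between-group comparison of the assessment of disease response at 48 weeks will be performed using a Wilcoxon-Mann-Whitney test". It is run at two-sided α = 0.05, with no stratum term, and is reported with a 95% confidence interval for the Mann-Whitney parameter. Section 13.6 matches it: "the null hypothesis for the Wilcoxon-Mann-Whitney test is defined according to the Mann-Whitney parameter", comparing a random person on elotuzumab with a random person on placebo regardless of stratum. So does section 13.7: "The sample size for Part 2 was determined by specifying the natural parameter to the Wilcoxon-Mann-Whitney test", with δ = 0.75, N = 63 (42 + 21) and 90% power from Noether's formula.

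The stratified test appears only in section 13.4.3: "analysis of the primary endpoint will be repeated as a van Elteren test with a covariate for the stratification factor". Under the fixed sequence in section 13.4.4, "if the between-group comparison of disease response at 48 weeks reaches statistical significance, a comparison of the rates of complete remission" follows. That comparison is the unstratified one. The documents do not say why the unstratified test was preferred.

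**The concern.** The sponsor chose disease history as its one stratification factor and then left it out of the one p-value that decides Part 2 and gates the key secondary endpoint. If newly-diagnosed and relapsing participants differ in outcome, an unstratified rank test counts that difference as noise. When allocation is balanced within strata, its null variance is also too large, so its actual type I error falls below 5%. Either way power is lost, in a trial with 21 controls. The van Elteren test is already in the plan, so recovering the power is a matter of which test is named primary.

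**Working it through.** **1. The plan's own figure.** Inputs from sections 13.4.2 and 13.7: two-sided α = 0.05, power 90%, δ = 0.75, fraction on elotuzumab c = 2/3. Noether's formula:

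N = (z₀.₉₇₅ + z₀.₉₀)² / [12 c(1 − c)(δ − 0.5)²] = (1.960 + 1.282)² / [12 × 2/3 × 1/3 × 0.25²] = 63.04 (using unrounded z values).

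Power at N = 63 is 89.98%. The stated sample size and power reproduce.

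**2. Model for the comparison.** N = 63, 2:1, two strata, 20,000 simulated trials per scenario (Monte Carlo SE about 0.001 to 0.003 for power and 0.0015 for size). The tie-corrected Wilcoxon-Mann-Whitney test (WMW) is compared with van Elteren, stratum weights 1/(n_k + 1). Assumptions not in the documents:

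- a four-level outcome (0, 50, 75, 100% improvement) from a cumulative-logit model, with control probabilities 40/20/15/25% midway between strata;
- strata shifted by plus or minus half the stratum log-odds ratio (LOR);
- strata of 32/31 or 52/11, with blocks of 3 or no balance enforced within strata (42/21 overall only). Blocks of 6 gave the same pattern as blocks of 3.

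**3. Power, WMW vs van Elteren.**

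| Scenario | LOR 0 | LOR 1.0 | LOR 1.5 | LOR 2.0 |
|---|---|---|---|---|
| Marginal δ 0.75, 32/31, blocks of 3 | 0.956 vs 0.954 | 0.962 vs 0.968 | 0.971 vs 0.981 | 0.976 vs 0.988 |
| Marginal δ 0.75, 32/31, no balance | 0.957 vs 0.954 | 0.960 vs 0.968 | 0.963 vs 0.979 | 0.961 vs 0.987 |
| Marginal δ 0.70, 32/31, blocks of 3 | 0.803 vs 0.800 | 0.817 vs 0.837 | 0.829 vs 0.869 | 0.842 vs 0.906 |
| Marginal δ 0.70, 52/11, blocks of 3 | 0.801 vs 0.799 | 0.829 vs 0.840 | 0.855 vs 0.878 | 0.890 vs 0.924 |
| Within-stratum treatment LOR fixed at 1.6, 32/31, blocks of 3 | 0.896 vs 0.894 | 0.867 vs 0.884 | 0.830 vs 0.871 | 0.767 vs 0.852 |

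Losses in points, by subtraction across the four columns:

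- row 1: −0.2, 0.6, 1.0, 1.2;
- row 2: −0.3, 0.8, 1.6, 2.6;
- row 3: −0.3, 2.0, 4.0, 6.4;
- row 4: −0.2, 1.1, 2.3, 3.4;
- row 5: −0.2, 1.7, 4.1, 8.5.

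In the last row the marginal δ itself falls (0.723, 0.712, 0.700, 0.684). Part of the WMW decline comes from that; only the gap between the two tests is due to ignoring the strata.

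**4. Type I error, 32/31.** With blocks of 3, WMW gives 0.051, 0.044, 0.033, 0.025 across the four LORs. Without within-stratum balance it gives 0.048 to 0.051. Van Elteren gives 0.048 to 0.052.

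**5. A second outcome model.** With a normal outcome, 50/50 strata, blocks of 3 and a *within-stratum* δ of 0.75 (6,000 trials per scenario), power is:

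| Stratum difference | WMW | van Elteren |
|---|---|---|
| 0 SD | 93.3% | 92.7% |
| 0.5 SD | 91.6% | 92.1% |
| 1.0 SD | 88.7% | 92.3% |
| 1.5 SD | 81.1% | 92.0% |

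If the *marginal* δ is held at 0.75 instead, both tests are higher: 94.1% vs 96.6% at 1.0 SD. Simulated power above Noether's 90% when the factor is not prognostic is no contradiction, because Noether's formula uses the null variance.

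**The case against.** The strongest reply is that the plan is internally coherent. The test, interval, hypothesis and sample size all use one marginal parameter, size is controlled, and the stratified result will be reported anyway. On that marginal definition, the loss at the target effect is at most 1.2 points with blocking, and both tests exceed 95% power. The larger losses need a true effect below target, near-equal strata and strong prognosis. A stratum LOR of 2.0 means an odds ratio of about 7.4, which under the model puts placebo 0% improvement at about 20% in one stratum and 64% in the other. No section reports any outcome difference by disease history. The 2.6-point figure assumes no balance within strata, which sits badly with stratified randomisation. Finally, moving to van Elteren changes the estimand and drops an interval method that has a published reference, and the gated Fisher test would remain unstratified.

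Most of this stands as a description of size and cost. It makes the point an efficiency improvement and the larger figures sensitivity scenarios. It does not remove the asymmetry: about 1 point or less lost if the factor is irrelevant, several points gained if it matters and the effect is modest. Reporting van Elteren as supportive does not help if the primary p-value just misses, because only the primary test opens the gate.

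**Conclusion.** The concern holds, as an efficiency point that should be acted on but does not threaten validity. At the plan's marginal δ of 0.75 with blocked allocation, the loss from ignoring the strata is about 1 point or less. At marginal δ of 0.70 it is about 0 to 6 points with equal strata and 0 to 3 with a 52/11 split. It reaches about 9 points in the most extreme scenario, with a fixed within-stratum effect. Under blocking the unstratified test can run as low as about 2.5% actual type I error; without blocking it stays near 5%. The mismatch between design and analysis is certain from the documents. The size is a range, because prognostic strength, stratum split, block design and outcome distribution are all assumed.

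**What to change.** Before unblinding:

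- **Section 13.4.2:** make the van Elteren test, stratified by newly-diagnosed versus relapsing disease, the primary test at two-sided 0.05. In section 13.4.3, keep the unstratified WMW as supportive, so the marginal summary is still reported.
- **Section 13.6:** restate the null as δ_S = Σ w_k δ_k = 0.5, with weights w_k proportional to n_Ek n_Pk / (n_k + 1), normalised to sum to 1.
- **Interval:** report δ_S with a 95% confidence interval from a method named in advance, for example a stratified proportional-odds analogue of the current interval. State how it relates to the test, since the current interval is tied to the unstratified one.
- **Section 13.4.3:** carry the stratified test through the missing-data, tipping-point, per-protocol and elevated-IgG4 analyses. State that a stratum containing only one arm contributes nothing.
- **Section 13.4.4:** the gate then follows the stratified p-value. N = 63 can stand.

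The cost is modest and needs no new data. The hypothesis, estimate, interval and repeated analyses must be re-specified together, the estimand moves from a marginal to a stratum-weighted probability, and small subgroups may have sparse strata. If the sponsor prefers to keep the marginal estimand, the reason should be recorded.

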13.4.3 Supportive Analyses of the Primary Endpoint

A supportive analysis of the primary endpoint will consider participants who drop out of the study prior to reaching week 48 without evidence of disease flare, initiation of non-protocol therapy, or other indications of increased disease activity as missing-completely-at-random (MCAR). Descriptive statistics and the Wilcoxon-Mann-Whitney test will be repeated in the subgroup of the mITT population excluding participants with data MCAR. A masked data review panel will evaluate participant disposition and all disease activity assessments in a blinded manner to define the types of missing data. In addition, analysis of the primary endpoint will be repeated as a van Elteren test with a covariate for the stratification factor of newly-diagnosed versus relapsing disease at study entry. As an additional supportive analysis which does not assume data are MCAR, a two-dimensional tipping point analysis of missing data will be conducted. Additional details on supportive analysis will be specified in the Statistical Analysis Plan.

Supportive analyses of the primary endpoint will be repeated in the PP populations and as a preplanned subgroup analysis in participants who are identified as having elevated serum IgG4 level prior to initiation of study therapy. The subgroup is defined as any serum IgG4 concentration greater than 1.5 times the upper limit of normal that is obtained within 6 months of the Baseline visit or at the baseline assessment of Serum IgG subclasses.

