11.2 Participant Withdrawal Criteria

Participants may be prematurely terminated from the study for the following reasons:

- The participant elects to withdraw consent from all future study activities, including follow-up.
- The participant is "lost to follow-up" (i.e., no further follow-up is possible because attempts to reestablish contact with the participant have failed).
- The participant dies.
- The Investigator no longer believes participation is in the best interest of the participant.
- The study is stopped by the sponsor.

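### The supportive MCAR analysis classes drop-outs by disease activity alone, so deaths and adverse-event withdrawals with quiet disease are deleted although the loss may be treatment-related

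*Combined protocol and SAP*

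**What the plan says.** The primary analysis (Section 13.4.2) compares percent improvement in the Responder Index at week 48 using a "Wilcoxon-Mann-Whitney test with a two-sided Type I α of 0.05". Anyone who drops out before week 48, for whatever reason, is scored as 0% improvement.

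Section 13.4.3 then relaxes that rule. Drop-outs "without evidence of disease flare, initiation of non-protocol therapy, or other indications of increased disease activity as missing-completely-at-random (MCAR") form a separate class, and the descriptive statistics and the test are "repeated in the subgroup of the mITT population excluding participants with data MCAR". A masked panel reviews disposition and disease activity assessments to decide the type of missing data. The same section plans a two-dimensional tipping point analysis that does not assume MCAR, and leaves further detail to a Statistical Analysis Plan. The supportive analyses are to be repeated in the per-protocol population and in the subgroup with elevated IgG4.

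Section 11.2 lists the ways out of the study. One is "The participant dies"; others are withdrawal of consent and the investigator's judgement that participation is no longer in the participant's interest. Section 6.6 separately expects participants who stop study drug to remain in follow-up, and Section 11.1 follows Part 2 participants for up to 48 weeks unless consent is withdrawn.

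**The concern.** MCAR means that the chance of being missing does not depend on treatment or on outcome. The absence of flare, rescue or disease activity does not establish that. It says the participant did not leave because IgG4-RD was active; it says nothing about whether they left because of the study drug. A fatal infection, or a withdrawal of consent after an adverse event, meets the written criterion whenever the disease happened to be quiet.

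The protocol gives some reason to expect such losses. In the largest myeloma trial it cites (Section 5.1.3), Grade 3 to 4 infections were reported in 28% against 24.3% and fatal infections in 2.5% against 2.2%, both higher with elotuzumab added. That population and background therapy differ from this trial, so an excess here is plausible but not established.

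What is at stake is how a supportive result is read. If the deletion analysis agrees with or improves on the primary result, it may be taken as showing that the 0% rule is harmlessly conservative. Part of that agreement could come from removing participants whom the drug harmed.

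**Working it through.** **The plan's own figures.** Section 13.7 targets a Mann-Whitney parameter of 0.75 with 2:1 allocation and states that 63 participants "would provide 90% power to detect the target effect-size". By Noether's formula with c = 2/3:

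N = (1.960 + 1.282)² / [12 × (2/3) × (1/3) × 0.25²] = 10.507 / 0.16667 = 63.04.

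Power at N = 63 is 0.8998. Full enumeration of Fisher's test for 25% against 65% (21 and 42 participants) gives 0.8261, against the stated 0.826. Both figures reproduce, so the arm sizes of 42 and 21 are used below.

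**Does a death fall under the rule?** The Section 13.4.3 criterion has three elements: flare, non-protocol therapy, and other signs of increased activity. Section 11.2 makes death and withdrawal of consent exits from the study. Neither section makes an exception for death or an adverse event. Read as written, such an exit with quiet disease is classed as MCAR and deleted.

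**Size of the effect.** The documents give no drop-out rate and no response distribution, so both are assumed. Let dE and dP be the shares of each arm lost in this way, dc the parameter among the remaining participants (the deletion result), and pE0 and pP0 the shares of those participants scored 0%. With the losses scored 0%, the parameter is

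(1−dE)(1−dP)·dc + dE(1−dP)·½·pP0 + (1−dE)dP·(1−½·pE0) + ½·dE·dP.

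*Illustration A.* Remaining participants at 0/50/100% improvement: elotuzumab 20/15/65%, placebo 60/15/25%.

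- Deletion: 0.15×0.60 + 0.65×0.75 + ½(0.20×0.60 + 0.15×0.15 + 0.65×0.25) = 0.5775 + 0.1525 = 0.73.
- Four elotuzumab losses, none on placebo: (38/42)×0.73 + (4/42)×½×0.60 = 0.660 + 0.029 = 0.69.
- Six and none: (36/42)×0.73 + (6/42)×0.30 = 0.626 + 0.043 = 0.67.
- None and two: (19/21)×0.73 + (2/21)×(1 − ½×0.20) = 0.660 + 0.086 = 0.746. Deletion is now the lower figure.

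In simulation with the tie-corrected test, the chance of p < 0.05 was about 79% with 0% scoring against 91% with deletion for four elotuzumab losses, and about 69% against 90% for six. With a weaker effect (25/20/55% against 50/20/30%) and four losses, the parameters are 0.61 and 0.65, and the chances were 33–34% against 52–56% across simulation runs.

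*Illustration B.* Completers' parameter set at the design value 0.75, with pP0 = 0.39 and pE0 = 0.12. These shares are borrowed from the relapse and failure rates in Section 1.1.2 as rough stand-ins.

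| Losses (elotuzumab + placebo) | Scored 0% | Deleted | Deletion minus 0% scoring |
|---|---|---|---|
| 2 + 0 | 0.724 | 0.75 | +0.026 |
| 4 + 0 | 0.697 | 0.75 | +0.053 |
| 6 + 0 | 0.671 | 0.75 | +0.079 |
| 4 + 2 (equal rates) | 0.716 | 0.75 | +0.034 |
| 0 + 2 | 0.768 | 0.75 | −0.018 |

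For 4 + 0 the difference runs from +0.043 to +0.062 as pP0 goes from 0.60 to 0.20. With no treatment effect (0.50, and 39% at zero in both arms), equal rates give a difference of 0.000, 4 + 0 gives +0.029 and 0 + 2 gives −0.029.

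**False positives.** With no effect among completers and 4 + 0 losses, the simulated chance of a significant result favouring elotuzumab was 0.7% with 0% scoring and 2.5% with deletion. The nominal one-sided level is 2.5%. Here the lost participants were a random subset as regards response.

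**The case against.** Much can fairly be said for the plan.

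- Stopping the drug is not leaving the study. Under Sections 6.6 and 11.1, participants who discontinue for toxicity are followed to week 48, so they have an observed score, or 0% if they flare or use non-permitted therapy. This stands. A reader might infer that everyone with elotuzumab toxicity is deleted; only those who die or also leave the study are.
- The tipping point analysis is designed for missingness that is not MCAR and can differ by arm. This stands in part. It covers the concern from another side, but the MCAR analysis still yields its own p-value, repeated in two further populations.
- The masked panel sees disposition and may well consider why someone left. That is possible, but the only written criterion does not use the reason, and no sentence tells the panel to keep deaths or adverse-event withdrawals as non-response. Blinding protects against classification by arm; it does not supply a missing criterion.
- The missing detail may be settled in the Statistical Analysis Plan. No separate plan text is among the documents, and the MCAR definition itself is already fixed in Section 13.4.3.
- Tolerability would not be hidden: disposition is summarised and safety endpoints are compared between arms (Sections 13.4.4 and 13.4.5). This stands.

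A reader might also infer that the analysis is biased towards elotuzumab outright, or that it inflates the false-positive rate. The documents support neither. The direction depends on where the losses fall, and the simulated null stayed at the nominal 2.5%. The higher chance of significance with deletion largely reflects removal of the 0% penalty, which is what relaxing that rule does. Bias in the effect among completers would also need the lost participants to differ from them in response, on which the documents are silent.

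**Conclusion.** The point holds as a mislabelled exclusion rule in one supportive analysis. Section 13.4.3 treats absence of disease activity as sufficient for MCAR, and so deletes deaths and adverse-event study withdrawals with quiet disease. That label is not justified for them, whichever arm they come from.

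The numerical consequence is conditional. With 2 to 6 of 42 such losses on elotuzumab and none on placebo, deletion raises the Mann-Whitney parameter by about 0.03 to 0.08 relative to 0% scoring (Illustration B; 0.69 to 0.73 for four losses in Illustration A). At equal rates the difference is smaller if the drug works and nil if it does not, and it changes sign when losses are mainly on placebo. The loss counts and response distributions are assumptions throughout.

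The trial's main conclusion is not at risk. The primary and key secondary analyses count every drop-out as non-response, and nothing is gated on this supportive result.

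**What to change.** In Section 13.4.3, and in the Statistical Analysis Plan where the detail is carried, limit the MCAR exclusion to drop-outs with a documented reason unrelated to treatment or disease, such as relocation or site closure. Keep deaths and study withdrawals related to an adverse event at 0% improvement in this analysis. Instruct the masked panel to classify on the reason for leaving as well as on disease activity, and report drop-out reasons by arm beside the result. The change should be made before unblinding.

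The cost is a sentence or two of text, with no added participants, visits or assessments. Slightly fewer participants will be excluded, and the supportive estimate may be a little less favourable.
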